1. SYNOPSIS

| | |
|---------------------------------|---|
| Study title | Luxembourg cohort of positive patients for COVID-19: a stratification study to predict severe prognosis |
| Study acronym | Predi-COVID |
| Version Number | 6.1 |
| Indication | COVID-19 infection |
| Rationale and background | 
Pandemics are large-scale outbreaks of infectious disease that can greatly increase morbidity and mortality over a wide geographic area and cause significant economic, social, and political disruption. A major pandemic can overwhelm the capacity of outpatient facilities, emergency departments (EDs), hospitals, and intensive care units, leading to critical shortages of staff, space, and supplies with serious implications for patient outcomes. The World Health Organization (WHO) declared COVID-19 a pandemic on March 11, with more than 300,000 people infected worldwide, as of March 23 2020. By March 23 2020 Luxembourg Ministry of Health has reported over 800 confirmed cases and 8 deaths.
 
Studies on epidemiological and clinical characteristics of adults with COVID-19 show that compared to women, men are more infected and the median age is 49.0 years. Common symptoms at onset of illness are fever, cough, dyspnea and myalgia or fatigue; less common symptoms were sputum production, headache, haemoptysis and diarrhea. Complications included acute respiratory distress syndrome, anaemia, acute cardiac injury and secondary infection. The risk for serious disease and death in COVID-19 cases increases with age. As of 23 March 2020, no vaccine has been successfully developed for COVID-19. The treatments are mainly symptomatic and supportive (only true for mild cases, severe cases have bacterial coinfections, so treatment includes antibiotics and also antivirals now (Kaletra)).
 
Children seem less often affected or develop more often the asymptomatic, aspecific and mild variant of the COVID-19 disease. Recent observations have demonstrated that not all children escape critical illness (example: Pediatric Multisystem Inflammatory syndrome- PIMS) . Clinical characteristics of the disease in children may differ from the adult disease and even more important the critical illness may and or may not be caused by the same pulmonary symptomatology. Whether rare immune mechanisms (IEI - inborn errors of immunity, host genetic susceptibility in innate immunity -related genes) or environmental factors are involved in these cases is unknown. Risk factors for severe disease in children need to be elucidated.
 
We determined that identifying profiles of patients predictive of more severe prognosis would be key to clinical management and would support more efficient public health measures. The purpose of this project is the identification of clinical and socio-demographic characteristics as well as the pathogen and/or host predictive biomarkers for the severity of the disease. We are aiming to better understand the heterogeneity observed in disease severity through a stratification approach of the cohort in Luxembourg.
 |
| Objectives | The study aims at identifying factors associated with the COVID-19 disease severity. COVID-19 patients with severity criteria will be compared to patients with mild disease managed at home. |

| | |
|----------------------------|---|
| | A deep phenotyping related to the symptoms of the disease as well as biosampling allowing for laboratory-based and computational analytics will be performed. |
| Evaluation criteria | Severity of symptoms will be evaluated by the occurrence of an hospitalisation, the duration of the hospitalisation, the occurrence of ICU (or equivalent structures) stay, the duration of ICU, the need for supplemental oxygen, the need for ventilation and the duration of both, the need for a transfer to another hospital, the impact of infection on daily activities. As knowledge on covid is evolving very quickly, additional criteria may have to be added. |
| Study design | Predi-COVID is a prospective cohort study composed of adults and children positively tested for COVID-19 in Luxembourg, followed digitally for monitoring participants' health evolution and symptoms at home. Participants will be actively followed for 14 days from the time of confirmation of diagnosis, whether they are at the hospital or at home in isolation or quarantine. Short evaluations will be also performed at week 3 and week 4 and then monthly for a period up to 12 months to assess potential long term consequences of COVID-19. The last monthly questionnaire will be more detailed to provide a specific focus on long-COVID symptoms evaluation and will be completed at M12, M15 and M24.. All participants will be followed digitally and a subsample will participate in a sample collection. |
| Intervention | For every adult (a "case") tested positive by RTqPCR, up to 45 mL of blood will be taken, a nasal swab and an oropharyngeal swab will be performed, an induced sputum (or saliva), hair sample and a stool samples will be recovered at the inclusion. As follow-up, 6 months, 15 months and 24 months after inclusion, the same sampling will be performed. Two additional sampling visits will be proposed to adult participants with a reinfection or a post-vaccination infection at 3 weeks and at 2 months. For every child tested positive by RTqPCR, up to 50 mL of blood will be taken, a nasal swab, oro- and naso-pharyngeal swabs, induced sputum or saliva, hair sample, as well as a stool sample will be obtained at inclusion. The follow up visits at 6, 15 and 24 months after inclusion, will include the same samples. For patients at home, an experienced nurse from CIEC will perform the sampling, using all the required precautions and protections in the actual context. For hospitalised patients, a simplified sampling strategy will be put in place and adapted to the patient state, the workload of staff and adapted constantly depending on the evolution of the epidemy. Below is described the maximal sampling strategy. |
| Study timelines | 
 ● Recruitment period: up to 29 months (March 2020-August 2022) - to be adapted to the evolution of the epidemiological situation) First patient in: March 2020 ● Follow-up period : max 24 months ● Analysis of results and study report: 3 months ● Global duration: 54 months (to be adapted on the duration of the epidemiological situation) |
| Population | Predi-COVID Inclusion criteria: |

| | |
|--|---|
| | 
 • Signed informed consent form • Adult (≥ 18 years old), child and adolescent (0-17 years old) patients with confirmed SARS-CoV-2 infection as determined by PCR, performed by one of the certified laboratories in Luxembourg • Hospitalized or at home 
Exclusions criteria :
 
 • Patients not understanding French or German • |
| Patient withdrawal criteria | Transfer outside Luxembourg if no information can be collected in the receiving country. |
| Number of patients/ participants | 
The objective is to recruit virtually all COVID-19 positive persons in Luxembourg.
 
A sub-sample of a minimum of 200 COVID-19 positive persons in Predi-COVID study would allow to find a risk ratio of severe disease above 2 for the selected risk factor with a power of 80% when the prevalence of the disease is above 7%.
 
A minimum of 100 COVID-19 positive children would allow to find a risk ratio of severe disease above 3.2 for the selected risk factor with a power of 80% when the prevalence of the disease is above 7%.
 |
| Safety | No AE/SAE reporting is planned in this study since no interventional medication involved. |
| Statistical methods and data analysis | 
Descriptive statistics will be produced for hospitalisation, intensive care / resuscitation admission, ventilation, their duration, death and severity of the disease. Other variables including potential prognostic factors of the disease will also be described with mean (+- STD) or frequencies (%) as adequate. Statistical models will be used to study whether the risks of hospitalisation, intensive care admission or intubation as well as death are associated with a specific risk factor. adjustment will be done on age, gender and other potential confounding factors.
 
Further stratification of the patient cohort will be performed through Machine learning techniques to include biological and other omics measurements. According to a deep phenotyping of the symptoms of the disease as well as biosampling allowing for laboratory-based and computational analytics, a stratification approach will include data-driven tools and allow to define disease trajectories that will be translated into clinical and/or biomarker-defined subgroups.
 |
| Interim Analyzes | Regular interim analyses will also be performed to inform policy stakeholders. It will be mainly descriptive statistics on the main endpoints defined above. |
| Regulatory | 
The study will be submitted for approval at MS* and CNER**.
 
The study will follow the new General Data Protection Regulation (GDPR) of 27 April 2016.
 
Written informed consent will be obtained before enrolment in the study.
 
*Ministry of Health, **National Research Ethics Committee
 |

| | |
|-------------------------------|--|
| 
Ancillary study
 | 
An ancillary study will be added (Predi-COVID-H). For patients included as well as subjects living with positively tested patients on the basis of a volunteer informed consent.
 
Predi-COVID-H is an ancillary cohort study composed of Household members of index cases to monitor symptoms and disease outbreak in this high-risk population. For every asymptomatic member of the family of a “case” included in the Predi-COVID sub-sample (a “contact”), clinical as well as socio-economic characteristics will be collected. Biological samples will also be collected at the same time as the “case” visit by nurses and up to 50 ml of blood, nasopharygeal and oropharyngeal swabs, stool, saliva and hair samples will be taken at baseline for adults and children. According to the new recommendations of the Health Directorate, all Household contacts of positive cases are invited by the Sanitary Inspection to be tested 5 days after the diagnostic test of the “index case”. In case of positive result, the “contact” will be proposed to be enrolled in the Predi-COVID study. Otherwise, a second visit will be planned 6 months later, to collect blood, nasopharygeal and oropharyngeal swabs, stool, saliva and hair samples. All “contacts” will be followed digitally.
 
Predi-COVID-H inclusion criteria:
 
 ● Adult and children (0-17 ans) house members of COVID-19 positive participants. 
Exclusions criteria :
 
 ● Patients not understanding French or German 
Sample size: A minimum of 100 participants (adults and children) will be included in the sub-study on house-members. The sample size and the sampling strategy may have to be adapted to the rapidly evolving knowledge on COVID-19.
 |
|-------------------------------|--|

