7.1 Data collection and sample collection (for the sub-sample only)

The samples and data collected during the study course are described in the table below. The participants will be able to participate either in data collection only or in both data and sample collection. For sample collection they can choose to do all or part of the sampling.

| Predi-COVID | | | | | | | | |
|---|--|---|--|------------------|--|------------------|-----------------------------------|-----------------------------------|
| | Screening | Inclusion | Baseline visit | Visit (3 weeks)* | Visit (2 months)* | Visit (6 months) | Visit (15 months) | Visit (24 months) |
| Eligibility assessment | x | | | | | | | |
| Informed consent | x (oral consent to be contacted by LIH) | x (e-consent for data collection) | X Written consent for sample collection, scanned on site and stored electronically at LIH | | | | | |
| Clinical data (ISARIC protocol CRF data) | | x Daily data collection for up to 30 days for hospitalized patients or once at baseline for patients at home | | | | | | |
| Online questionnaires (for adult participants and children >10 years) | | Daily data collection for 14 days and weekly at weeks 3 and 4 | | | Monthly follow up (1 to 11 months after inclusion), detailed questionnaire Long Covid at M12 | | Detailed questionnaire long covid | Detailed questionnaire long covid |

| | | | | | | | | |
|---|--|---|---|---|---|---|---|---|
| CoLive LIH smartphone application (optional, for adults and children >10 years) | | Regular voice recordings + short questionnaires | | | | | | |
| Blood sample : up to 50mL (for children, volume adapted to child's weight) | | | x | x | x | x | x | x |
| Stool sample | | | x | | | x | x | x |
| Induced sputum or saliva | | | x | | | x | x | x |
| Nasopharyngeal swab | | | x | x | | x | x | x |
| Oropharyngeal swab | | | x | | | x | x | x |
| Hair sample | | | x | | | x | x | x |

- only for ADULTS, with a re-infection or an infection post-vaccination

[1] See « Annexe 2 de l'arrêté du 17 février 2021 fixant la liste des recherches mentionnées au 2° de l'article L. 1121-1 du code de la santé publique » - https://www.legifrance.gouv.fr/loda/article_lc/LEGIARTI000033546109/2016-12-07/

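### The adult blood maximum is 45 mL in the synopsis but 50 mL in the section 7.1 schedule, and the synopsis omits the weight condition that both schedules set for children

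*Protocol*

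**What the plan says.** The protocol gives a maximum blood volume in four places.

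- **Section 1, Synopsis, Intervention row, adult cases:** "up to 45 mL of blood will be taken". The sampling repeats: "As follow-up, 6 months, 15 months and 24 months after inclusion, the same sampling will be performed". The row also offers two extra sampling visits, at 3 weeks and 2 months, to adults with a reinfection or a post-vaccination infection.
- **Section 1, Synopsis, Intervention row, child cases:** "For every child tested positive by RTqPCR, up to 50 mL of blood will be taken". Again the sampling repeats: "The follow up visits at 6, 15 and 24 months after inclusion, will include the same samples". No weight condition is given.
- **Section 1, Synopsis, Ancillary study row, household contacts:** "up to 50 ml of blood, nasopharygeal and oropharyngeal swabs, stool, saliva and hair samples will be taken at baseline for adults and children". No weight condition is given here either.
- **Section 7.1 schedule (cases) and section 7.3 schedule (household contacts):** both blood rows carry the same limit, "up to 50mL (for children, volume adapted to child's weight". In 7.1 the row is marked at baseline, 3 weeks, 2 months, 6, 15 and 24 months. The 3-week and 2-month visits are for reinfected or post-vaccination adults only.

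The inclusion criteria admit children from birth to 17 years.

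**The concern.** A ceiling on a repeated blood draw should have one value for each group of participants. Here adult cases have two. For children, a condition that limits the draw stands in the schedules but not in the summary of the same procedure.

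This is more than tidiness, because blood sampling is a core part of what the study does to participants. Section 9 classes the study as interventional on the ground that it collects biosamples. Section 2.7 lists pain, bruising, tiredness or fainting, and infection as risks of the blood sample. The draw recurs over two years. Read literally, the synopsis sets a flat ceiling for every child, infants included, and places it above the ceiling for adult cases without giving a reason. I found no statement of which text governs when the synopsis and a schedule differ.

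**Working it through.** No power, sample size or error rate is involved. The check is a side-by-side reading followed by multiplication.

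**Step 1. Set the limits side by side.**

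| Group | Synopsis | Schedule | Same number? | Same weight rule? |
|---|---|---|---|---|
| Adult cases | 45 mL | 50 mL (7.1) | No | Not applicable |
| Child cases | 50 mL, no weight rule | 50 mL, adapted to weight (7.1) | Yes | No |
| Adult contacts | 50 mL | 50 mL (7.3) | Yes | Not applicable |
| Child contacts | 50 mL, no weight rule | 50 mL, adapted to weight (7.3) | Yes | No |

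Only one cell is a numerical conflict: adult cases. The two child rows show an omitted condition under the same number.

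**Step 2. Size of the adult conflict.**

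Per draw: 50 − 45 = 5 mL.

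Four standard draws (inclusion, 6, 15 and 24 months):
- synopsis: 4 × 45 = 180 mL
- section 7.1: 4 × 50 = 200 mL
- gap: 200 − 180 = 20 mL

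Six draws (the four above plus 3 weeks and 2 months, for a reinfected or post-vaccination adult):
- synopsis: 6 × 45 = 270 mL
- section 7.1: 6 × 50 = 300 mL
- gap: 300 − 270 = 30 mL

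The six-draw figure assumes that the 45 mL cap covers the two extra visits. The synopsis states no separate volume for them.

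Section 6 describes the basic scheme as two visits, baseline and 6 months. On that count the gap is 2 × 5 = 10 mL. The number of standard draws is therefore itself not uniform in the protocol. The 20 mL figure follows the synopsis and the 7.1 schedule, which agree on four.

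**Step 3. Order of the ceilings within the synopsis.**

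Child case minus adult case: 50 − 45 = 5 mL. Adult contact minus adult case: 50 − 45 = 5 mL. The synopsis explains neither difference.

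**Step 4. Does other text in the synopsis close the gap?**

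The Intervention row says that sampling of hospitalised patients is simplified and adapted to their condition. That sentence does not cover home sampling, and a patient's condition is not a weight rule. The row also announces a maximal sampling strategy. That wording does not reconcile the adult figures, because both 45 and 50 mL are worded as maxima.

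**The case against.** The strongest reply is that a synopsis is a summary and the schedules are the working text. Both schedules carry the weight rule in the same words, every figure is prefaced as an upper limit, and a weight-adapted volume fits inside a 50 mL ceiling. Home sampling is done by an experienced nurse, and section 7.1 lets participants accept all or part of the sampling.

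Much of this stands for children. A reader might infer that the child limits contradict each other, or that the protocol has no weight protection for infants. The documents support neither. The child ceiling is 50 mL throughout, and the weight condition is present in both schedules; it is stated inconsistently, not absent. Nor do the documents show that staff sample from the synopsis rather than the schedule, or that anyone has been over-sampled. Multiplying the child ceiling by the number of visits would give only a nominal total that ignores the rule in 7.1, so no cumulative child figure is offered here. A reader might also suppose that the difference decides which assays can be run. Section 7.2 lists assays without any volume per assay, so that cannot be shown.

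The reply does not remove the adult conflict. Two upper limits for the same draw remain two limits, and calling one text a summary does not help when the protocol does not say which prevails.

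Some material is out of view: the figure summarising the sampling strategy, the consent pages, and a legal text cited under the 7.1 table. Whether any of them states a volume is unknown. None would cure the mismatch between the two passages as they stand.

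**Conclusion.** The point holds in two parts of different kinds.

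1. **A numerical contradiction for adult cases.** The maximum is 45 mL in the synopsis and 50 mL in section 7.1: 5 mL per draw, 20 mL over four standard draws, and up to 30 mL over six draws if the synopsis cap extends to the two extra visits.
2. **An omitted condition for children.** The ceiling agrees everywhere at 50 mL, but weight adaptation appears only in the 7.1 and 7.3 schedules. It is missing from the synopsis for both child cases and household contacts. One consequence is that the synopsis, read alone, gives child cases a higher ceiling than adult cases.

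This is an internal inconsistency in a procedure that bears on participant safety. It does not touch the endpoints or the analysis. It should be corrected, but it is not evidence that children are unprotected in the working schedules. Which volume is right is not judged here.

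**What to change.** Reconcile four places: the synopsis Intervention row, the synopsis Ancillary study row, the section 7.1 schedule and the section 7.3 schedule. Each age group should have one stated maximum and one stated rule, worded the same way wherever it appears. State whether the adult maximum also applies to the 3-week and 2-month visits. Then check that the information sheets and consent forms for cases and for contacts carry the same limits.

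The volume and the form of the weight rule are for the sponsor, the paediatric investigators and the ethics committee. The cost is a wording amendment to the protocol and, if the consent documents turn out to differ, to those as well. No analysis changes.

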2. INTRODUCTION AND RATIONAL

2.1 Background

In December 2019 the first case of pneumonia caused by a novel betacoronavirus, the 2019 novel coronavirus (2019-nCoV), was reported from the city of Wuhan, Hubei Province in Mainland China (3). The disease quickly spread to other parts of China and across the globe. The World Health Organization (WHO) declared COVID-19 a pandemic on March 11 (2), with more than 200,000 people infected worldwide, as of March 19 2020. Pandemics are large-scale outbreaks of infectious disease that can greatly increase morbidity and mortality over a wide geographic area and cause significant economic, social, and political disruption. A major pandemic can overwhelm the capacity of outpatient facilities, emergency departments (EDs), hospitals, and intensive care units, leading to critical shortages of staff, space, and supplies with serious implications for patient outcomes (1).

By March 19 2020 Luxembourg Ministry of Health has reported 335 confirmed cases and 4 deaths. In an attempt to limit the speed of COVID-19 propagation, several European countries, including Luxembourg, have ordered an emergency confinement of their population. This is a crucial step to decrease the speed of the infection spreading as much as possible. These measures are giving more time to the health care providers and scientific community to be prepared and to identify an adapted therapy. This time should also be used to improve our understanding of the disease development, its outcome and heterogeneity.

2.2 Rationale

The pathogen for the new outbreak has been identified as a novel enveloped RNA betacoronavirus2 that has currently been named severe acute respiratory syndrome coronavirus 2 (SARS-CoV-2), which has a phylogenetic similarity to SARS-CoV (1). Studies on epidemiological and clinical characteristics of patients with COVID-19 show that compared to women, men are more infected and the median age is 49.0 years (1, 4). Common symptoms at onset of illness are fever, cough, dyspnoea and myalgia or fatigue; less common symptoms were sputum production, headache, haemoptysis and diarrhea. Complications included acute respiratory distress syndrome, anaemia, acute cardiac injury and secondary infection (4). The risk for serious disease and death in COVID-19 cases increases with age (5). In the United States case-fatality percentages increased with increasing age, from no deaths reported among persons aged ≤ 19 years to highest percentages (10%–27%) among adults aged ≥ 85 years (5). The findings from the United States are similar to data from China, which indicated $>80\%$ of deaths occurred among persons aged ≥ 60 years (5). As of 19 March 2020, no vaccine has been successfully developed for COVID-19. The treatments are mainly symptomatic and supportive. The study by Huang et al. reported that the most common complications in patients with 2019-nCoV infection were acute respiratory distress syndrome, followed by anemia, acute heart injuries, and secondary infections.

Due to the rapid spread of COVID-19, we determined that identifying profiles of patients predictive of more severe prognosis would be key to clinical management and would support more efficient public health measures. Although there have been some studies on epidemiological and clinical characteristics of patients with COVID-19, there is a lack of research investigating the prognostic factors for the severity of the disease. The accurate prognostic evaluation of COVID-19 can provide a guiding basis for active and effective management of the outbreak.

The purpose of this project is the identification of patients clinical and socio-demographic characteristics as well as pathogen and/or host predictive biomarkers for the severity of the disease. We are aiming to better understand the heterogeneity observed in disease severity through a stratification approach of the cohort in Luxembourg.

Pathogen biomarkers include the SARS CoV-2 strain (sequence) (6, 7). Host biomarkers include clinical phenotypic characteristics, serological history, co-infections, genetic polymorphisms, immune cell phenotypic markers, immune circulating markers, fecal virome and hormones/glucocorticoid concentration. Applicable guidelines have been issued by the WHO and the CDC (8, 9) and quality control materials have been produced by commercial suppliers (10). Previously deposited patent applications include many details on laboratory protocols (11). Very recently, specific preanalytical and analytical guidelines have also been published (12).

Study design: This is a prospective cohort study. The study (Predi-COVID) will include all adults >18 years with confirmed COVID-19 infection (positive by RTqPCR test). Clinical data collection and monitoring of participants' health evolution and symptoms will be proposed to all participants. A subsample of a minimum of 200 patients will be invited to participate in the biological samples collection.

